7.3 Assignment to study groups

For the field tests the allocation is single group; therefore, all the test subjects will be assigned to the same group. The initial field test will be with the RMD and the second with the IMD, as it will take time

to have the IMD made by the lab.

For the lab tests the assignment to the test condition order will be randomized by the statistician. The test condition order will be randomized using a latin square design. This will minimize bias created when one test condition is tested in the final or last position all the time.

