8.2.2 Control Intervention

The RMD is worn over the ear with a piece (earmold or dome) that is worn inside the ear canal. The RMD is the current marketed device. They will use the RMD programmed for the current study for approximately 10 +/- 7 days and then switch to the IMD. They will compare the IMD to the RMD after the 10-day field test with the IMD. Normal use of a hearing device is 8-10 hours per day. They will wear the RMD and the IMD for the same amount of time each day. The hours of daily use will be controlled with a data logging feature in the software that programs the hearing aids.

The study procedure will use a single group assignment design. The subjects will have already worn the RMD during the first period, and will then all wear the IMD at the same time during the second period. As stated previously, the device is non-invasive and requires no surgical procedure. The RMD device is placed over the ear and the dome or earmold is placed inside the ear canal. The subjects themselves will place the device in their ears each morning and remove them each night for sleeping. The test subjects are experienced users of the BTEs, same style as the RMD, and will have been placing it on their ears for at least 6 months before beginning the current study. They will have been given an Instructions for Use booklet when fitted with the devices that explains how to insert the device and provides further instructions concerning cleaning, battery changing, and warnings.

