10. SAFETY

10.1 Medical Device Category C studies

All adverse events (AE) including all serious adverse events (SAE) are collected, fully investigated and documented in the source document and appropriate case report form (CRF) during the entire study period, i.e. from patient's informed consent until the last protocol-specific procedure, including a safety follow-up period. Documentation includes dates of event, treatment, resolution, assessment of seriousness and causal relationship to device and/or study procedure.

The information on AEs is systematically collected by the clinician at each study visit. They will follow the procedures outlined in SOP-Medical Device Incident Reporting. The subjects are asked to keep a diary and write down any unexpected events. During the regular clinic visits the subjects are then asked questions about the event to gather details and to determine the severity of the event. If a subject reports pain that results in the inability to use the device he will be withdrawn from the study in order to avoid any pain from using the device and to remove partial data from the study. For reports of pain caused by insertion or the dome itself, the problem can be addressed in the clinic. For example, a different style or size of dome can be placed on the hearing aid, and re-training of insertion can be performed with the subject to avoid wrong or forceful insertion of the device. For reported pain they will be advised to not wear the device for 24 hours before resuming use.

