- Any pre-existing disease or medical condition that remains stable and does not worsen during the course of study participation.
- Situations in which an adverse change did not occur, e.g., hospitalizations for unrelated cosmetic elective surgery or for social and/or convenience reasons.

Serious Adverse Event (SAE)

Adverse event that:

- results in death, or
- led to a serious deterioration in health that either:
 - results in a life-threatening illness or injury, or
 - results in a permanent impairment of a body structure or a body function, or
 - required in-patient or prolonged hospitalisation, or
 - results in medical or surgical intervention to prevent life threatening illness, or
- led to fetal distress, death or a congenital abnormality or birth defect. [ISO 14155: 3.37].

This includes device deficiencies that might have led to a serious adverse event if a) suitable action had not been taken or b) intervention had not been made or c) if circumstances had been less fortunate. These are handled under the SAE reporting system. A planned hospitalization for pre-existing condition, or a procedure required by the protocol, without a serious deterioration in health, is not considered to be a serious adverse event.

Device deficiency

Inadequacy of a medical device related to its identity, quality, durability, reliability, safety or performance, such as malfunction, misuse or use error and inadequate labelling [ISO 14155: 3.15].

Health hazards that require measures

Findings in the trial that may affect the safety of study participants and, which require preventive or corrective measures intended to protect the health and safety of study participants [ClinO Art. 37].

Severity of adverse events/adverse device effects

The severity of clinical AEs is graded on a three-point scale: mild, moderate and severe, and reported in the CRF. If the severity of an AE worsens during medical device administration, only the worst intensity should be reported on the CRF. If the AE lessens in intensity, no change in the severity is required.

Mild: Event may be noticeable to subject; does not influence daily activities; the AE resolves spontaneously or may require minimal therapeutic intervention;

Moderate: Event may make subject uncomfortable; performance of daily activities may be influenced; intervention may be needed; the AE produces no sequelae.

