11.4.5 Safety analysis

Safety analysis is foreseen to be accomplished by a questionnaire completed by the participants during the trial. Clinical judgement from the PI will be used for the safety evaluation.

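### With every subject wearing the RMD first and the IMD second, a single worst grade per adverse event does not show under which device a continuing event worsened, and section 11.4.5 does not name the adverse-event records as a source for the safety analysis

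*Protocol*

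**What the plan says.** The order of wear is fixed. Section 7.3 states: "The initial field test will be with the RMD and the second with the IMD". Section 8.2.2 confirms it, in a sentence that closes by naming the later of the two periods: "The subjects will have already worn the RMD during the first period, and will then all wear the IMD at the same time during the". Only the order of the speech-test conditions is randomised.

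Adverse events are collected from consent to the last study procedure (section 10.1), so one collection window covers both devices. On severity, section 10.1.1 says "If the severity of an AE worsens during medical device administration, only the worst intensity should be reported on the CRF" and "If the AE lessens in intensity, no change in the severity is required".

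On what is collected, section 10.1 says "The information on AEs is systematically collected by the clinician at each study visit" and "Documentation includes dates of event, treatment, resolution, assessment of seriousness and causal relationship to device and/or study procedure". Section 9.2.3.1 adds a description of the event, its duration, how often it occurred, and whether it caused discomfort, pain or disturbed hearing.

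On analysis, section 11.4.5 consists of two statements: "Safety analysis is foreseen to be accomplished by a questionnaire completed by the participants during the trial" and "Clinical judgement from the PI will be used for the safety evaluation".

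**The concern.** The worst-grade rule is a common convention and does little harm when a subject receives one treatment. Here each subject receives two devices in the same order, and the safety objective (section 4.4) concerns the second one. The informative fact about an event that continues through the switch is whether it got worse on the IMD. One grade per event discards that, and none of the listed data items asks for the date of worsening or the device worn at that time.

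The schedule marks device administration at visits 1 and 2, that is, for the RMD and then the IMD. The phrase about worsening while the device is administered is therefore most naturally read as spanning both periods.

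Section 11.4.5 adds a second weakness. It makes a positive statement about where the safety analysis comes from, and the records that section 10 takes care to collect are not in it. If it is followed literally, a by-device reading of safety depends on the topics that the questionnaire happens to ask about.

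**Working it through.** The protocol gives no safety figure to reproduce, so the check sets the rules side by side.

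**Step 1: what the worst-grade rule keeps.** Take one event present in both periods, graded mild, moderate or severe in each. There are 3 × 3 = 9 pairs (RMD-period grade, IMD-period grade). The recorded grade is the maximum of the two: the rule on worsening raises it, and the rule on lessening leaves it where it is.

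| Recorded grade | Pairs (RMD period, IMD period) that produce it | Number | Of these, worse under the IMD |
|---|---|---|---|
| Mild | mild–mild | 1 | 0 |
| Moderate | mild–moderate, moderate–mild, moderate–moderate | 3 | 1 |
| Severe | mild–severe, moderate–severe, severe–mild, severe–moderate, severe–severe | 5 | 2 |

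Mild under the RMD then severe under the IMD gives the same recorded grade as severe under the RMD then mild under the IMD. The maximum is preserved in all nine cases; the period in which it occurred is not. These are counts of patterns, not probabilities.

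**Step 2: whether another required item restores the period.**

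- *Event dates and resolution (10.1).* These place the onset and the end. An event with onset after the IMD fitting at visit 2 is correctly placed. An event with onset before it has no required date of worsening.
- *Causal relationship (10.1).* This is required towards the device or procedure, but the text does not say that it is rated separately for RMD and IMD. The graded scale in 10.1.1 is headed as applying to serious events.
- *Event description (9.2.3.1).* It covers duration, frequency and consequences, not the device worn.

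So the gap is confined to events that start under the RMD, continue past visit 2 and then change grade.

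**Step 3: the analysis source against the foreseeable events.** Sections 5.3 and 9.2.3 list the questionnaire's safety topics: feedback or whistling, distortion or artefacts, discomfort, muting or shutting off, unexplained signals, and loud sounds. Section 10.1 lists foreseeable adverse events. Some overlap, such as discomfort and loss of amplification. Skin reaction, and domes or filters coming off in the ear, are not among the listed topics. They would be captured as adverse events under section 10, which 11.4.5 does not name.

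**The case against.** A fair defence has several parts, and much of it stands.

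- **Harm is not erased.** The rule keeps the worst grade and never downgrades. A reader might infer that harm is hidden; the text does not support that. Only the link between grade and device period is lost.
- **No rule assigns events by onset date.** A reader might infer that worsening under the IMD is counted against the RMD. That would follow only from an onset-date convention, which the protocol does not state. Section 10.1.1 defines an adverse device effect by relation to the investigational device, so the PI can classify a worsening as IMD-related whenever the event began.
- **The change may be traceable.** Events are reported at visit 2, when the switch happens. CRFs are completed immediately after the visit (12.1.2), and the audit trail keeps the original and altered values with their time (12.2.2). A grade raised after visit 3 could be recovered from it. It is not, however, part of the final record, and its time stamp is that of data entry, not of the worsening.
- **The analysis is not the questionnaire alone.** PI judgement is the second element, and the PI is the listed author of the adverse-event fields (12.1.1). The product questionnaire is answered separately for each device and compared (9.2.2), and its discomfort item might pick up some skin reactions. Missing questionnaires can be sought by post (11.5), which weakens any inference that early stoppers are simply lost.
- **A by-device table is ordinary SAP content.** This is correct, and its absence from the protocol is not the point. The point is what 11.4.5 affirmatively states as the basis of the analysis.

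One might also try to size the problem with zero-event limits: 1 − 0.05^(1/16) = 17.1% for 16 subjects and 1 − 0.05^(1/20) = 13.9% for 20 (one-sided 95%, exact). These describe the small sample, not this defect. The rule deletes no event, and the protocol sets no safety threshold that a reassigned event could cross, so it cannot be said that a conclusion would change.

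**Conclusion.** The point holds in a limited form. In a fixed-order, two-device design, a single worst grade does not show under which device a continuing event worsened, and the stated basis of the safety analysis omits the records best placed to show it. The worst grade is kept, events that first arise under the IMD are placed correctly by their dates, and PI judgement, the per-device questionnaire and the audit trail offset part of the loss.

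The size cannot be given as a rate. It depends on how many events begin under the RMD, continue past visit 2 and change grade, which the protocol does not let one estimate; over field periods this short it is likely to be few. Sample size, type I error and power are untouched. The conclusion assumes that the severity rule is applied to one continuing event across both devices, and that the CRF carries no item on worsening beyond those listed in the protocol. It is worth acting on because the safety aim is to detect new IMD risks before release and the remedy is cheap.

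**What to change.** **Section 10.1.1.** Keep the worst-intensity rule within a device period. Add that, when an event worsens after the switch to the IMD, the date of worsening, the new grade and the device worn are recorded, or a new entry carrying these is opened and linked to the first.

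**Section 11.4.5.** State that CRF-recorded adverse events, adverse device effects and device deficiencies are summarised by device worn at onset or worsening, for all subjects who wore that device, alongside the questionnaire and the PI's judgement. The layout can be left to the SAP.

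**Cost.** One additional CRF item and one table. The date and device at worsening are not among the items now listed, so this is new data collection, but visits 2 and 3 already include adverse-event questioning and no extra visit is needed.

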10.1.2 Reporting of (Serious) Adverse Events and other safety related events

Reporting to the Sponsor

The following events are to be reported to the Sponsor within 24 hours upon becoming aware of the event:

- All SAEs
- Health hazards that require measures
- Device deficiencies

The Sponsor will evaluate SAEs with regard to causality and seriousness. Device deficiencies are assessed regarding their potential to lead to an SAE.

Reporting to Authorities:

In Category C studies it is the local Investigator's responsibility to report **serious adverse events** in Switzerland which are

- related or possibly related to the medical device under investigation
- related or possibly related to study procedures
within 7 days to the local Ethics Committee. The Sponsor-Investigator reports within the same timeline to Swissmedic (incl. events from abroad).
- **Health hazards** that require measures are reported within 2 days

All in the trial involved other Ethical Committees receive all mentioned reportable SAEs and health hazards having occurred in Switzerland via the Sponsor-Investigator within the same timeline. All participating investigators are informed regarding the occurrence of a health hazard.

Periodic safety reporting

In Category C studies a yearly safety update-report is submitted by the Investigator to the Ethics Committee and by the Sponsor-Investigator to Swissmedic.

10.1.3 Follow up of (Serious) Adverse Events

The adverse event shall be followed by the PI until its resolution or until the adverse event is recognized as permanent or stable condition by the PI. Follow-up investigations may be necessary according to the PI's medical judgement. In this situation, the follow-up does not have to be documented in the CRF but must be noted in the source documentation.

In case of SAE / SADE the sponsor can be contacted following the list below. If the first person in the list cannot be timely contacted, the PI should try to contact the next and so on.

Contact order

Contact order	Name	Mobile	Office	E-Mail
1	[name]	[contact]	Head of SIV	[contact]
2	[name]	[contact]	Senior Director	[contact]

Table1. Contact information of the sponsor in case of SAE/SADE

11. STATISTICAL METHODS

The primary outcome is the objective speech testing results of the IMD compared with the RMD. It will be measured two times during the trial. Speech will be tested with the RMD and the IMD at the second and third appointments. Two speech tests, the OLSA (reference test) and the GÖSA, will be used and with three conditions: unaided, aided with the RMD, and aided with the IMD. Speech Reception Threshold (SRT) from a previous experiment (BF001-1611) with the RMD and the OLSA test will be used to determine the required sample size.

11.1 Hypothesis

There is little evidence from research literature and experience that with equivalent technology, the IMD might be superior to the RMD for speech reception thresholds. Benefit from a more closed fit might be partially compensated by the larger distance between microphone on the BTE placement. However, we can expect that the performance should be at least as good with the IMD.

SRT benefit expressed in terms of benefit with amplification ($SRT_{unaided} - SRT_{aided}$), will be used as primary outcome in the following hypothesis and sample size calculation. As there is no technical motivation to find a benefit with the IMD, the tested hypothesis should therefore focus on the non-inferiority of the IMD compared to the RMD:

H0: average benefit with the IMD (μ_{IMD}) is not non-inferior to the average benefit with the RMD (μ_{RMD})

$$\mu_{IMD} \leq \mu_{RMD} - \delta$$

H1: average benefit with the IMD (μ_{IMD}) is non-inferior to the average benefit with the RMD (μ_{RMD})

$$\mu_{IMD} > \mu_{RMD} - \delta$$

where δ is the non-inferiority margin.

The non-inferiority margin determination follows the guidelines of Flight & Julious (2016). The non-inferiority margin is defined to be the clinical acceptable difference allowing us to conclude that there is no difference between the treatments. We will base our reflexion on SRT benefit from the validation of the RMD to satisfy the following requirements:

- Assay sensitivity, the RMD should provide a benefit over the unaided condition. This can be verified by the achieved mean benefit of +4 dB SNR (SD = 0.8 dB SNR).
- Constancy assumptions, the IMD will be tested in the same conditions and the eligibility criteria are similar between both studies.
- Minimized bias, to reduce the influence of results variability from natural fluctuation the difference between conditions is used rather than absolute SRT results.

From the reference study, a significant and audible difference could be found between the tested devices. This was also reflected by a difference of 1.3 dB SNR (SD = 1.6 dB SNR) in the SRT scores. The OLSA test manufacturer states that the precision to determine the SRT lies around 1 dB for within subject measures. We can therefore set the non-inferiority margin to 1 dB SNR which correspond to a little bit less than 80 % of an audible effect measured with the test. With a non-inferiority margin of 1 dB, we are still ensuring that the IMD has a positive effect over the unaided condition.

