Background and Rationale:	
The benefits of amplification and accessories used with it outweigh any risks in mild to profound hearing-impaired subjects. Hearing aids constantly undergo incremental improvements from already marketed devices. The new devices are expected to perform as well or better than the previous devices.
 
Bernafon conducts clinical investigations to test whether the new technology provides the same or more benefit than previous Bernafon devices. Additionally, the aim of the testing is to grant quality control prior to product launch according to Bernafon development requirements.
 
The current study will evaluate a new hearing aid hardware. The firmware driving the hearing aid has already been sold on the market using the Behind-the-Ear (BTE) hardware for almost one year and will now be launched using the In-the-Ear (ITE) custom hardware. The goal is to evaluate the audiological performance, usability, feature function, and to identify unexpected or unwanted behaviour from the devices. The study plans to compare the two hardware styles regarding the benefit received from different microphone locations.
 
As human subjects are involved the validation falls under the definition of a clinical investigation. The validation will address the performance of the new chip using the ITE hardware, and ensure that there is no reduction in speech understanding between using the BTE and ITE hardware styles. Evaluating the overall performance of the Mermaid 9 ITE devices is important to validate that the end user is satisfied with the devices and that all user requirements are fulfilled. All features available in Mermaid 9 have been validated and are currently used on the market in Mermaid 9 BTE devices.

Objective(s):	
The purpose of this study is to show that the performance of the ITE device is as good as the performance of the marketed BTE device. Furthermore, speech and comfort should not be negatively affected by the different hardware style. The usability of the devices, i.e. that the end users are able to handle the devices, should be as good as the marketed BTE device, and there should be no artefacts or unwanted noises.

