8.1.1 Experimental Intervention (medical device)

The investigation product (IMD) is a medical device. It is a new version of a Bernafon hearing device. The name is Mermaid 9 ITE. The Mermaid 9 BTE style was released to the market in early 2017. The Mermaid 9 ITE does not deviate from the current commercial product except for the hardware style. The ITE is fitted completely in the ear canal and concha of the ear while the BTE style fits with the body of the device over the ear, and a dome or earmold inside of the ear canal. Performance of the IMD is expected to be the same as the RMD. They are non-invasive devices. The hearing aid is worn inside the ear canal and is made from non-toxic plastic with an acrylic coating. A comparison of the hardware styles is shown in Figure 1.

Figure 1. Mermaid 9 ITEs (left) and Mermaid 9 BTEs (right).

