11.2 Determination of Sample Size

The results with the IMD and the RMD are collected on the same subject. SRTs are continuous and normally distributed data. We can therefore apply the sample size determination for mean difference

on one sample.

The formula to compute the sample size is:

$$n = \left(\frac{\sigma(z_{1-\alpha} + z_{1-\beta})}{\delta} \right)^2$$

With n the sample size, σ the standard deviation from the population, δ the non-inferiority margin, α the type I error, and $1-\beta$ the power of the test.

With the following input: $\sigma = 1.6$ dB SNR, $\delta = 1$ dB SNR, $\alpha = 0.05$, and $1-\beta = 0.8$, we will need a sample size of 16 to satisfy the test hypothesis.

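### Section 11.1 attaches a conclusion of no difference to the 1 dB margin, but its one-sided hypothesis can show only that the IMD's mean benefit is less than 1 dB below the RMD's

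*Protocol*

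**What the plan says.** Section 11.1 defines benefit as unaided SRT minus aided SRT, so larger is better. It says that "the tested hypothesis should therefore focus on the non-inferiority of the IMD compared to the RMD". The null is that mean IMD benefit is at or below mean RMD benefit minus δ, and the alternative is that it is above that value. The margin is then fixed: "We can therefore set the non-inferiority margin to 1 dB SNR". In the sentence that defines it, the margin is described as a clinically acceptable difference "allowing us to conclude that there is no difference between the treatments".

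The synopsis, under Background and Rationale, says that the validation will "ensure that there is no reduction in speech understanding between using the BTE and ITE hardware styles". It mentions neither the margin nor the test.

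Other sections keep closer to the hypothesis. Section 5.1 speaks of a non-inferiority test, and section 11.4.2 compares the difference with the margin to test for non-inferiority. Section 11.4.3 treats superiority as a separate step that needs a confidence interval above zero. For the GÖSA, section 11.4 says that no margin can be computed, and 11.4.3 makes that analysis exploratory.

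**The concern.** Section 11.1 contains both a hypothesis and a conclusion, and the conclusion is not the one that the hypothesis tests. A one-sided test against minus 1 dB bounds the shortfall of the IMD and nothing else. A statement of no difference needs a bound on both sides, and even then only within a stated range. A statement of no reduction needs the lower confidence limit to reach zero, not minus 1 dB.

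What is at stake is the claim that the report may make. Section 4.1 describes the study as final validation before sales, and section 13 foresees communicating results outside the sponsor. If the wording of 11.1 carries into the report, a result that allows a loss just under 1 dB could be summarised as no difference. This is a conflict within the text, not a detail left to a statistical analysis plan.

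**Working it through.** **Inputs.** Margin δ = 1 dB, reference RMD benefit 4 dB, and a reference-study device difference of 1.3 dB with SD 1.6 dB (all 11.1). One-sided α = 0.05, power 0.80, paired design (11.2: "The results with the IMD and the RMD are collected on the same subject"). True difference 0, implicit in the formula and consistent with 8.1.1: "Performance of the IMD is expected to be the same as the RMD". Planned enrolment about 15 to 20 (synopsis).

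**1. Reproduce the planned sample size.** n = (σ(z₀.₉₅ + z₀.₈₀)/δ)² = (1.6 × (1.645 + 0.842)/1)² = 15.83, rounded up to 16. This matches 11.2. With one-sided α = 0.025 the same formula gives 20.09, so 21, which does not match. The design is therefore a one-sided 5% non-inferiority test.

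**2. What the alternative contains.** It holds for every true difference (IMD minus RMD) above −1 dB, with no upper limit.
- Share of the reference benefit: 1/4 = 25%, so a benefit only just above 3 of 4 dB still satisfies it.
- Share of the 1.3 dB difference that 11.1 describes as significant and audible: 1/1.3 = 77%.

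**3. How often non-inferiority is declared.** Noncentral t, SD 1.6 dB, one-sided 5%, noncentrality (true difference + 1)√n/1.6:

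| True difference (dB) | n = 16 | n = 20 |
|---|---|---|
| 0 | 77% | 85% |
| −0.25 | 56% | 65% |
| −0.50 | 33% | 38% |
| −0.75 | 15% | 17% |

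**4. Largest observed deficit that still passes.** The observed mean difference must exceed −1 + t₀.₉₅ × SD/√n.
- n = 16: −1 + 1.753 × 0.400 = −0.30 dB
- n = 20: −1 + 1.729 × 0.358 = −0.38 dB

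**5. Could a pass coincide with a significant deficit?** At SD 1.6 dB and n = 16, the IMD is significantly worse (two-sided 5%) only if the observed difference is below −0.85 dB. That fails non-inferiority, so the two cannot coincide. If the paired SD were 0.8 dB (an assumption, to show the range), an observed deficit between 0.43 and 0.65 dB at n = 16 would do both.

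**6. What a two-sided claim would need.** For equivalence within ±1 dB (two one-sided 5% tests, SD 1.6 dB, true difference 0, 80% power), n is about 22 by the normal approximation, (1.6 × (1.645 + 1.282)/1)² = 21.9, or 24 with the t distribution. At n = 16 the simulated power is about 54%. No finite sample supports a literal statement of no difference.

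**The case against.** The strongest reply is that the sentence in 11.1 carries its own qualifier. It defines a margin by clinical acceptability, so its natural meaning is no clinically relevant difference. The formal hypotheses are correctly one-sided and correctly named, and a statistician following section 11 would test and report non-inferiority. Section 11.4 already foresees a confidence interval. Section 11.1 also discloses the margin, the 4 dB benefit and the ratio of slightly under 80%.

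Much of this stands, and it limits the point to the stated conclusion. It does not remove the point: even with the qualifier, no relevant difference is a two-sided statement, and only one side is tested.

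A reader might infer three stronger things that the protocol does not support:
- **That passing the margin is said to guarantee no reduction.** The synopsis sentence is an aim that cites neither margin nor test. The link is only that the OLSA comparison is the one speech comparison of the devices with a pre-set hypothesis and margin, so nothing else in the plan could carry that aim.
- **That a worse device would be released under a no-reduction claim.** No section specifies such a release statement or makes release depend on the primary test.
- **That the pass rates at −0.25 or −0.50 dB are errors.** Under the stated alternative they are correct decisions, and accepting losses inside the margin is inherent in any non-inferiority trial.

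**Conclusion.** The point holds as a mismatch between the tested hypothesis and the stated conclusion. A successful test supports one statement: the mean IMD benefit on the OLSA is less than 1 dB SNR below the RMD benefit. It does not support no difference. The synopsis aim of no reduction is also stronger than the test can show; among the planned OLSA results, only the superiority step in 11.4.3 would exclude a reduction.

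The 25% bounds the true mean loss and relies on the 4 dB reference benefit applying in this trial. The pass rates and the observed limits of 0.30 to 0.38 dB rely on a paired SD of 1.6 dB and 16 to 20 analysed subjects. The mismatch itself relies on none of these figures. The hypotheses, the margin and the sample size of 16 are not called into question here.

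**What to change.** In section 11.1, replace the conclusion attached to the margin with: *the IMD is not worse than the RMD by 1 dB SNR or more in OLSA SRT benefit*. Align the synopsis aim on speech understanding with that wording. State that the estimated difference and its confidence interval accompany the claim wherever it is made.

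The cost is a slightly weaker stated claim. Hypotheses, margin, alpha, n = 16, visits and data collection do not change. If the sponsor wants to keep a two-sided claim, it would have to be framed as equivalence within a stated range and sized for that, at about 22 to 24 subjects for ±1 dB on the protocol's SD.
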